## 6. TREATMENT PLAN

### 6.1 Diagnostic Procedures

A PET-CT may be performed (optional) for diagnostic purposes and can be used for treatment planning with fusion.

## **6.2 Study Procedures**

**Upon confirmation of eligibility and enrollment in the study, the following will be completed:**

- 1) Demographics review, medical history and clinical exam
- 2) Review of concurrent medications
- 3) Vital signs, height and weight
- 4) Blood work per Standard of Care for immunotherapy used.
- 5) Plasma and Peripheral blood mononuclear cells will be collected and subsequently frozen for immune monitoring assays.

Blood chemistry and hematology assessments: must be performed at baseline, prior to each avelumab dose, at end of treatment visit and at 30 days post-treatment safety follow-up. Urine pregnancy test for women of childbearing potential must be performed at baseline and least every month during treatment. Free T4 and TSH must be performed at baseline and at least every 8 weeks during treatment and at end of treatment or 30 days post-treatment safety follow-up (if not performed in the previous 8 weeks). In addition, a CT Chest with contrast or MRI will be performed on Cycle 4 (+/- 4 days) of Avelumab treatment.

## **6.3 Therapeutic Procedures**

### **6.3.1 Avelumab Administration**

Each cycle of Avelumab is 14 days. Avelumab is administered on an outpatient basis. Avelumab 10mg/kg body weight, diluted with 0.45% or 0.9% saline solution, will be administered as a 60 minute intravenous (IV) infusion every 2 weeks, on day 1 of each cycle. No Avelumab dose reductions are permitted on this study. Specific instructions for the preparation infusion fluid and administration of infusion solution are provided in the Pharmacy Manual.

After the initial cycle, the patient will receive 5 additional cycles of adjuvant Avelumab per protocol for a total of 6 cycles. Patients will be evaluated for adverse events/toxicities after receiving the first dose of Avelumab.

### **6.3.2 SBRT Procedures**

Upon enrollment on the protocol patients will be seen by at least one of the Co-Investigator Medical Oncologists. As per standard of care a 4D CT simulation will be performed with fabrication of a radiation therapy immobilization device (such as a Vac-Lok) which will be custom made for each patient. The treating radiation oncologist will identify the location of the tumor. Gross tumor volume (GTV) delineation will be performed on sequential axial computed tomography images. An SBRT treatment plan will be developed based on tumor size and location. The radiation dose will be prescribed using the current clinical practice standard of care of either 12Gy x 4 fractions or 10Gy x 5 fractions at the discretion of the treating radiation oncologist.

Adjacent normal structures including but not limited to the chest wall, spinal cord, lung, airways at risk, vessels at risk, heart, esophagus, aorta, liver, and stomach within 5 cm of the GTV will be identified for the purpose of limiting incidental radiation to these structures.

The patient will receive the first fraction of SBRT within 3-10 days after starting the 1st cycle of Avelumab. SBRT will be administered using image-guidance as per standard of care. An Vac-Lok (or equivalent immobilization device such as Alpha-Cradle) will be used to minimize movement of the chest, spine, and abdomen during treatment. During treatment, cone beam images of the patient's body site of interest will be obtained. Cone beam scan will be obtained immediately prior to treatment and will be repeated until the treatment shift, required to align the Radiation planning scan and the cone beam scan performed on the day of treatment. Cone beam scanning is standard of care for definitive stereotactic body radiation therapy.

6.3.3 The SBRT dose constraints for surrounding critical structures are as follows

- ξ **chest wall at risk: V30<60; max point dose 48 Gy;**
  - ξ **spinal cord: V13.6 Gy<1.2cc; V 20.8 Gy<0.35cc; point max: 26 Gy**
  - ξ **great vessel at risk: V43 Gy<10cc; point max: 49 Gy**
  - ξ **esophagus at risk: V18.8 Gy<5cc; point max: 30 Gy**
  - ξ **airway at risk: V15.6 Gy<4cc; point max 34.8 Gy**
  - ξ **heart at risk: V28<15cc; point max< 34 Gy**
  - ξ **Combined lung constraints:**
    - **MLD <4 Gy**
    - **V20 <4%**
    - **V10 <12%**
    - **combined lung: V11.6 Gy<1500cc**
    - **combined lung: V12.4 Gy<1000cc**
    - **Ratio of Prescription Isodose Volume to the PTV volume <1.2**
    - **Ratio of 50% Prescription Isodose Volume to the PTV Volume varies.**
- Please refer to Table A below for guidance.**

**Table A: Conformality of Prescribed Dose for Calculations Based on Deposition of Photon Beam Energy in Heterogeneous Tissue**

PTV Volume (cc)	Ratio of Prescription Isodose Volume to the PTV Volume		Ratio of 50% Prescription Isodose Volume to the PTV Volume, R 50%		Maximum Dose (in % of dose prescribed) @ 2 cm from PTV in Any Direction, D 2cm (%)		Percent of Lung Receiving 20Gy Total or More, V 20 (%)	
	Deviation		Deviation		Deviation		Deviation	
	None	Minor	None	Minor	None	Minor	None	Minor
1.8	<1.2	<1.5	<5.9	<7.5	<50.0	<57.0	<10	<15
3.8	<1.2	<1.5	<5.5	<6.5	<50.0	<57.0	<10	<15
7.4	<1.2	<1.5	<5.1	<6.0	<50.0	<58.0	<10	<15
13.2	<1.2	<1.5	<4.7	<5.8	<50.0	<58.0	<10	<15

22.0	<1.2	<1.5	<4.5	<5.5	<54.0	<63.0	<10	<15
34.0	<1.2	<1.5	<4.3	<5.3	<58.0	<68.0	<10	<15
50.0	<1.2	<1.5	<4.0	<5.0	<62.0	<77.0	<10	<15
70.0	<1.2	<1.5	<3.5	<4.8	<66.0	<86.0	<10	<15
95.0	<1.2	<1.5	<3.3	<4.4	<70.0	<89.0	<10	<15
126.0	<1.2	<1.5	<3.1	<4.0	<73.0	<91.0	<10	<15
163.0	<1.2	<1.5	<2.9	<3.7	<77.0	<94.0	<10	<15

Note: For values of PTV dimension or volume not specified, linear interpolation between table entries is required.

#### 6.4 Follow-Up Procedures

Subsequent to SBRT, patients will be followed clinically, radiographically, and with bloodwork. A detailed medical and physical examination will be performed at 4 weeks, 8 weeks, and 16 weeks, 6 months, 12 months, 18 months, 24 months, 30 months, and 36 months. A complete blood count (CBC) and comprehensive chemistry panel and CT Chest with contrast will be performed at 6 weeks and 3 months and will continue at intervals of every 6 months until 2 years post SBRT treatment.

Recist 1.1 measurements at 6 months and 1 year and 2 years will be used to determine radiographic response for loco-regional control and relapse free survival.

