### 10. STUDY CALENDAR

Parameter	Pre TX	CBI Cycle#1, Day 1	SBRT 4-5 Fx~	CBI Cycle#2, Day 1	CBI Cycle#3, Day 1	CBI Cycle #4, Day 1	CBI Cycle #5, Day 1	CBI Cycle #6, Day 1	FU% 1 mo $\Sigma$	FU% 6wks $\Sigma$	FU% 2mo $\Sigma$	FU% 3mo $\Sigma$	FU% 6mo@	FU% 12mo@	FU% 18mo@	FU% 24mo@	FU% 30mo@	FU% 36mo@	
Informed Consent	X																		
Demographics	X																		
Med HX & Medication Rev	X								X		X	X	X	X	X	X	X	X	X
Physical Exam	X				X				X		X	X	X	X	X	X	X	X	X
Standard of Care Labs#	X	X +		X +	X +	X +	X +	X +	X	X	X	X	X	X	X	X	X	X	X
Serum Pregnancy Test	X																		
Urine Pregnancy Test				X		X		X											
Free T4 and TSH	X	X				X			X										
CT or MRI Chest Imaging	X					X $\Sigma$				X			X	X	X	X	X	X	X
CT Abd/Pelvis or PET Scan	X																		
Avelumab Administration ^		X		X	X	X	X	X											
Research Blood Draw	X*				X*														
Recist 1.1 Measurement	X												X	X	X	X	X	X	X
AE Evaluation	X	X	X	X	X	X	X	X	X	X	X	X	X	X	X	X	X	X	X

#: Standard of Care Labs include: CBC and CMP  
 + Prior to each Avelumab dose

@ +/- 10 day  $\Sigma$  +/- 4 days

^ Each cycle of Avelumab is 14 days. Drug is administered on day 1 of each cycle.  
 ~ SBRT: to be administered in 4-5 fractions at the discretion of the treating Radiation Oncologist  
 % Follow-up appointments will be scheduled based on date of SBRT completion. These will begin during Avelumab treatment.  
 \* indicates optional

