## 11. MEASUREMENT OF EFFECT

### 11.1 Antitumor Effect-Solid Tumors

For the purposes of this study, patients should be re-evaluated for response 6 months after the initial treatment, 12 months after treatment, and at 6 month intervals thereafter.

Response and progression will be evaluated in this study using the new international criteria proposed by the Response Evaluation Criteria in Solid Tumors (RECIST 1.1) Committee (30). Changes in only the largest diameter (unidimensional measurement) of the tumor lesions are used in the RECIST criteria.

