### **11.5.3 Clinical Response Parameters**

**Time to Local Progression (TTLP)** is defined as the elapsed time from the start of treatment to the date of documented local progression or death, whichever happens earliest.

**Relapse-Free Survival (RFS)** is defined as the time from starting treatment to the time of first documented tumor progression or death due to any cause, whichever occurs first. Death is considered as an event here. For subjects whose disease does not progress or who do not die, PFS will be censored at the time of the last visit.

**Time to Progression (TTP)** is defined as the time from starting treatment to the time of first documented tumor progression. Subjects who do not progress will be censored at the time of the last contact. In addition, death from any cause will also be censored.

**Overall Survival (OS)** is defined as the time from starting treatment until death due to any cause. For subjects who do not die, time to death will be censored at the time of last contact.

**Locoregional Control (LRC)** is defined as the time from starting treatment until local and/or regional relapse is documented

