### 15.5 Analysis of Secondary Objectives

- To determine whether SBRT combined with concurrent and adjuvant Avelumab results in improved loco-regional control, relapse free survival, and overall survival we will evaluate the recist criterion scans and survival rates at 6 months, 12 months and 24 months.
- To analyze whether SBRT combined with concurrent and adjuvant Avelumab impacts anti-tumor immune responses we will perform immunologic assays quantifying lymphocyte specificity and activation, including Immune cell Sequencing, ProtoArrays, Immunoassays, cell free DNA analyses, and multiparametric flow cytometry.
- Hazard rate estimates and 95% confidence intervals as well as Kaplan-Meier (KM) estimates will be used to summarize survival (OS), progression free survival (RFS), time to locoregional progression (TTLP) and time to distant progression (TTDP),

duration of response functions over time, and stable disease (SD). The median OS, PFS, TTLP, TTDP, and SD will be reported.

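### The sections disagree on which scans decide RFS (6, 12 and 24 months, or every 6 months) and on when CT ends; the sparser list dates year-2 relapse later, and the plan does not say whether the 24-month scan counts toward the 2-year rate

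*Combined protocol and SAP*

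**What the plan says.** Four places describe the assessments behind RFS, the Phase II primary endpoint.

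- **Section 6.4** (Follow-Up Procedures): "Recist 1.1 measurements at 6 months and 1 year and 2 years will be used to determine radiographic response" for loco-regional control and RFS. Month 18 is not listed. The same section orders chest CT at 6 weeks and 3 months, which "will continue at intervals of every 6 months until 2 years post SBRT treatment", while clinic visits run to 36 months.
- **Section 11.1:** "patients should be re-evaluated for response 6 months after the initial treatment, 12 months after treatment, and at 6 month intervals thereafter". Month 18 is included and no end is given. This section covers both response and progression.
- **Section 10** (Study Calendar): the rows "CT or MRI Chest Imaging" and "Recist 1.1 Measurement" carry unbroken marks over the 6-monthly columns to 36 months. Follow-up visits are timed from SBRT completion, with a window of 10 days either way from month 6 on.
- **Section 15.5:** for loco-regional control, RFS and overall survival, the plan is to "evaluate the recist criterion scans and survival rates at 6 months, 12 months and 24 months".

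Section 11.5.3 runs RFS from the start of treatment to first documented progression or death. For patients with neither, "PFS will be censored at the time of the last visit" (the sentence sits inside the RFS definition, so it is taken to mean RFS). Sections 15.1 and 15.2 name the endpoint as the RFS rate at a median follow-up of 2 years, with a null of 80% and a target of 90% at 2 years. No section says how the 24-month visit relates to that 2-year point.

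**The concern.** A relapse without symptoms is dated at the scan that shows it, so the list of qualifying scans partly determines the RFS times. Two lists are in force. A site following section 6.4 would have no RECIST reading between months 12 and 24; a site following section 11.1 or the calendar would have one at month 18. The resulting RFS times would not be comparable.

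The comparison is with a fixed historical 80%, and the effect sought is 10 percentage points. A dating rule that moves part of year-2 relapse past the 2-year mark could therefore take up much of that margin.

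There is a second mismatch after year 2. Under section 6.4 the visits continue for 12 months after the last CT, and censoring follows the visit. Unscanned time is then counted as relapse-free.

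**Working it through.** The plan gives no figure for the effect of the scan schedule, so there is none to reproduce. The inputs are its 80% null at 24 months (section 15.2), the two assessment lists, the two time origins and the visit window. Constant hazard is an assumption: S(t) = 0.8^(t/24).

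**1. How much relapse is at issue**

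- S(12) = 0.8^0.5 = 0.894 and S(18) = 0.8^0.75 = 0.846.
- First events in year 2: 0.894 − 0.800 = 0.094, of which about 0.049 fall in months 12–18 and 0.046 in months 18–24.

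**2. Dating delay**

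A year-2 relapse found only by scan waits for the next listed reading.

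| Readings used | Maximum delay | Mean delay |
|---|---|---|
| 6, 12, 24 months | 12 months | about 6 |
| 6, 12, 18, 24 months | 6 months | about 3 |

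**3. If the 24-month scan counts toward the 2-year rate**

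Every year-2 relapse is found by that scan on either list. A Kaplan-Meier simulation of 400,000 patients per scenario, with 10% and with 20% dropout, gave 0.800 on both lists under the null and 0.900 on both under the target. The rate is unchanged; only the dates move.

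**4. If RFS is read at exactly 24.0 months from treatment start**

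- SBRT begins 3–10 days after the first avelumab dose (section 6.3.2).
- It takes 4–5 fractions every other day (section 6.5), so the last is 6–8 days after the first.
- SBRT completion is therefore at day 3 + 6 = 9 to 10 + 8 = 18.
- With the window, the 24-month visit falls from 9 − 10 = −1 to 18 + 10 = +28 days around the 24.0-month date.
- If all combinations of start lag (8 values), fraction number (2) and window day (21) were equally likely, only 3 of 336 would fall on or before that date.

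Almost all 24-month scans would then come too late to count. Suppose that CTs between the listed RECIST dates are also ignored. Let f be the share of first events dated when they occur (deaths, symptomatic relapses) and L the last reading before month 24. Apparent RFS = 0.8 + (1 − f)(S(L) − 0.8).

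| f (assumed) | Without month 18 (L = 12) | With month 18 (L = 18) |
|---|---|---|
| 0 | 0.894 | 0.846 |
| 0.25 | 0.871 | 0.834 |
| 0.50 | 0.847 | 0.823 |

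Simulation of 56-patient trials with 10% dropout and the visit window gave similar means: 0.891, 0.868 and 0.844 without month 18, and 0.842, 0.829 and 0.821 with it.

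**5. False-positive rate, for illustration only**

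Section 15.2 names a one-sided t-test at 0.10 and gives no decision rule. Take 50 evaluable patients (56 × 0.9 = 50.4) and an exact binomial rule, with f from 0 to 0.50 as above.

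| Rule | Size at a true 80% | Without month 18 | With month 18 |
|---|---|---|---|
| At least 45 of 50 | 0.048 | 0.565 to 0.204 | 0.197 to 0.102 |
| At least 44 of 50 | 0.103 | 0.727 to 0.341 | 0.332 to 0.194 |

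**6. Year 3**

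Under section 6.4 no CT is planned in months 24–36, while visits continue at 30 and 36 months. A patient seen at month 36 and not known to have relapsed contributes 12 unscanned months as relapse-free time. This affects the curve after month 24, not the 2-year rate.

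**The case against.** The case against a serious defect is strong, and much of it stands.

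- **Nothing need be lost.** A reader might infer that the sparser list hides second-year relapse. The documents do not support that: the list contains a 24-month scan, and if that scan counts the 2-year rate is identical on both lists. The relapses are recorded late.
- **The 84–89% figures stack assumptions.** They need a strict 24.0-month reading, CTs between listed dates ignored, and at most half of events exactly dated. Section 6.4 itself orders CT every 6 months to 2 years, and the RFS definition counts any first documented progression. Read literally, 3 months and then every 6 months puts CTs at 9, 15 and 21 months. If those count, the reading at 24.0 months is 0.8^(21/24) = 0.823, a bias of about 2 points.
- **Adding month 18 does not cure the problem.** On the strict reading, 6-monthly assessment still gives up to about 85%. The remainder comes from the undefined landmark and the two time origins.
- **False-positive rates are not firm.** They move with the test assumed. Relapse in the historical series may also have been dated by scans; the plan gives no imaging schedule for those sources, and similar delay there would shrink the relative bias.
- **Section 15.5 may only name reporting times.** That is a fair reading, but the conflict between sections 6.4 and 11.1 remains.

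A reader might also infer that the calendar omits the 3-month CT ordered in section 6.4. That cannot be established. As extracted, the CT and RECIST rows carry one mark more than the header has columns, so the 3-month column cannot be read reliably. The marks for months 6 to 36 are present on either alignment.

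What survives is the conflict in the text, the later dating under the sparser list, and the absence of a rule that secures the harmless reading.

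**Conclusion.** The concern holds as a conflict that bears on the primary endpoint and should be resolved before analysis. It is not evidence that the 2-year rate is wrong. The certain effect is on dating: year-2 scan-detected relapse is recorded up to 12 months late on the sparser list against 6 on the other. The effect on the 2-year rate ranges from none, if the 24-month scan counts, to about 9 percentage points at most (0.894 against 0.800), if it does not, intervening CTs are ignored and every event is found by scan. With the 18-month reading that maximum falls to about 5 points (0.846 against 0.800). Both upper figures assume constant hazard, and both shrink as more events are exactly dated. The documents do not say which reading applies. The stop in CT at 2 years, combined with censoring at the last visit, affects only the year-3 part of the curve.

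**What to change.** - Reconcile sections 6.4 and 15.5 with section 11.1 and the calendar, so that every scheduled 6-monthly assessment, including month 18, feeds RFS and loco-regional control. State that progression documented between those dates also counts, on the date it is documented.
- Reconcile the CT end date between section 6.4 and the calendar, and give the CT months explicitly so that the 6-monthly interval has one reading.
- State that the 24-month assessment, with its visit window, counts toward the 2-year RFS rate. This removes the bias that the 18-month reading only reduces.
- In section 11.5.3, censor RFS at the last disease assessment instead of the last visit.

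The cost is protocol wording. The 18-month assessment is already in section 11.1 and the calendar. Some patients will be censored slightly earlier.

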#### 6.5 Duration of Therapy

The patient will receive 4-5 fractions of SBRT radiation total administered every other day. The patient will receive Avelumab administered every 2 weeks for a total of 6 cycles. Thus the total duration of therapy is expected to last approximately 3 months.

#### 6.6 Duration of Follow-Up

It is anticipated that this study will last 3 years.

#### 6.7 Criteria for Removal of Subjects from Study Treatment and Study

- Unacceptable adverse events grade IV or greater with an attribution of possibly related while on CBI or after SBRT.
  - Subject withdraws consent for follow-up;
  - Subject is lost to follow-up;
  - Subject dies;
  - Study is terminated for any reason.
- ξ The patient has a confirmed positive serum pregnancy test;

ξ General or specific changes in the patient's condition render the patient unacceptable for further treatment in the judgment of the investigator;

ξ Administrative Decision

Subject can elect to discontinue treatment at any time. If participants withdraw from the study, they will be followed for survival data.

## 6.8 Alternatives

The study has been designed to minimize potential risks to participants. This is primarily through designation of a dose range shown to be safe in previous SBRT trials and careful patient monitoring. The risks of Avelumab have been reported and are detailed in the manufacturer treatment guidelines. Risks to confidentiality will be minimized by having access to study records available only to the investigators with the exception of the standard clinical records (lab values, dictations, operative notes, etc) which are maintained through the UCSD Health System and Moores Cancer Center.

Standard therapies for early stage NSCLC include definitive surgical resection with or without systemic chemotherapy versus definitive radiation therapy alone. Only patients who are medically inoperable or those who refuse surgery after thoracic surgery consultation will be enrolled in this study.

## 6.9 Permitted and Prohibited Concomitant Therapies

### Permitted concomitant therapy

Concomitant medication also includes all prescription, over-the-counter (OTC), herbal supplements, blood transfusions, and IV medications. The patient needs to notify the investigational site about any new medications he/she takes after the start of the study drug.

All concomitant medications received within 28 days before the first dose of trial treatment and 30 days after the last dose of trial treatment should be recorded in the patient's medical record.

### Prohibited concomitant therapy

Patients are prohibited from receiving the following therapies during the Screening and Treatment Phase of this trial:

- Antineoplastic systemic chemotherapy or biological therapy.
- Immunotherapy not specified in this protocol.
- Chemotherapy not specified in this protocol.
- Investigational agents other than avelumab.
- Live vaccines within 30 days prior to the first dose of trial treatment and while participating in the trial. Examples of live vaccines include, but are not limited to, the following: measles, mumps, rubella, varicella/zoster, yellow fever, rabies, BCG, and typhoid vaccine.
- Systemic glucocorticoids for any purpose other than to modulate symptoms from an adverse event of suspected immunologic etiology.

Patients who, in the assessment by the investigator, require the use of any of the aforementioned treatments for clinical management should be removed from the treatment portion of the study. Patients may receive other medications that the investigator deems to be medically necessary.

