## 5.2 Exclusion Criteria

Subjects are not eligible for the trial if they fulfill any of the following exclusion criteria:

- 5.2.1 Prior organ transplantation, including allogeneic stem cell transplantation
- 5.2.2 Significant acute or chronic infections including, among others:
- Known history of testing positive for human immunodeficiency virus (HIV) or known acquired immunodeficiency syndrome (AIDS)
  - Known history of testing positive for HBV surface antigen and / or confirmatory HCV RNA (if anti-HCV antibody tested positive)
- 5.2.3 Active autoimmune disease that might deteriorate when receiving an immunostimulatory agent:
- a. Subjects with diabetes type I, vitiligo, psoriasis, hypo- or hyperthyroid disease not requiring immunosuppressive treatment are eligible
  - b. Subjects requiring hormone replacement with corticosteroids are eligible if the

steroids are administered only for the purpose of hormonal replacement and at doses  $\leq 10$  mg or 10 mg equivalent prednisone per day  
c. Administration of steroids through a route known to result in a minimal systemic exposure (topical, intranasal, intro-ocular, or inhalation) are acceptable

- 5.2.4 Current use of immunosuppressive medication, EXCEPT for the following: a. intranasal, inhaled, topical steroids, or local steroid injection (eg, intra-articular injection); b. Systemic corticosteroids at physiologic doses  $\leq 10$  mg/day of prednisone or equivalent; c. Steroids as premedication for hypersensitivity reactions (eg, CT scan premedication).
- 5.2.5 Clinically significant (i.e., active) cardiovascular disease: cerebral vascular accident/stroke ( $< 6$  months prior to enrollment), myocardial infarction ( $< 6$  months prior to enrollment), unstable angina, congestive heart failure ( $\geq$  New York Heart Association Classification Class II), or serious cardiac arrhythmia requiring medication.
- 5.2.6 Known severe hypersensitivity reactions to monoclonal antibodies (Grade  $\geq 3$  NCI CTCAE v 4.03), any history of anaphylaxis, or uncontrolled asthma (that is, 3 or more features of partially controlled asthma)
- 5.2.7 Persisting toxicity related to prior therapy of Grade  $>1$  NCI-CTCAE v 4.03; however, alopecia and sensory neuropathy Grade  $\leq 2$  is acceptable
- 5.2.8 Pregnancy or lactation
- 5.2.9 Known active alcohol or drug abuse

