**Any Grade 2 ADR should be managed as follows:**

- If a Grade 2 ADR resolves to Grade  $\leq 1$  by the last day of the current cycle, treatment may continue.
- If a Grade 2 ADR does not resolve to Grade  $\leq 1$  by the last day of the current cycle, infusions should not be given on the following cycle. If at the end of the following cycle the event has not resolved to Grade 1, the subject should permanently discontinue treatment with avelumab ADR (except for hormone insufficiencies, that can be managed by replacement therapy; for these hormone insufficiencies, up to 2 subsequent doses may be omitted).
- Upon the second occurrence of the same Grade 2 ADR (except for hormone insufficiencies that can be managed by replacement therapy) in the same subject, treatment with avelumab has to be permanently discontinued.
- Infusion-related reactions, hypersensitivity reactions (Grades 1 to 4), and tumor lysis syndrome should be handled according to guidelines provided.

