Grade 2 AST or ALT > 3.0 to ≤ 5 x ULN and / or total bilirubin > 1.5 to ≤ 3 x ULN	Delay avelumab therapy Increase frequency of monitoring to every 3 days	If returns to Baseline: Resume routine monitoring, resume avelumab therapy If elevations persist > 5 to 7 days or worsen: 0.5 to 1 mg/kg/day methylprednisolone or oral equivalent and when LFT returns to Grade 1 or Baseline, taper steroids over at least 1 month, consider prophylactic antibiotics for opportunistic infections, and resume avelumab therapy
Grade 3 to 4 AST or ALT > 5 x ULN and / or total bilirubin > 3 x ULN	Discontinue avelumab therapy Increase frequency of monitoring to every 1 to 2 days 1.0 to 2.0 mg/kg/day methylprednisolone IV or IV equivalent Add prophylactic antibiotics for opportunistic infections Consult gastroenterologist Consider obtaining MRI/CT scan of liver and liver biopsy if clinically warranted	If returns to Grade 2: Taper steroids over at least 1 month If does not improve in > 3 to 5 days, worsens or rebounds: Add mycophenolate mofetil 1 gram (g) twice daily If no response within an additional 3 to 5 days, consider other immunosuppressants per local guidelines
Endocrine irAEs		
Endocrine Disorder	Management	Follow-up
Asymptomatic TSH abnormality	Continue avelumab therapy If TSH < 0.5 x LLN, or TSH > 2 x ULN, or consistently out of range in 2 subsequent measurements: include T4 at subsequent cycles as clinically indicated; consider endocrinology consult	
Symptomatic endocrinopathy	Evaluate endocrine function Consider pituitary scan Symptomatic with abnormal lab / pituitary scan:	If improves (with or without hormone replacement):

	Delay avelumab therapy 1 to 2 mg/kg/day methylprednisolone IV or by mouth equivalent Initiate appropriate hormone therapy No abnormal lab / pituitary MRI scan but symptoms persist: Repeat labs in 1 to 3 weeks / MRI in 1 month	Taper steroids over at least 1 month and consider prophylactic antibiotics for opportunistic infections Resume avelumab therapy Subjects with adrenal insufficiency may need to continue steroids with mineralocorticoid component
Suspicion of adrenal crisis (for example, severe dehydration, hypotension, shock out of proportion to current illness)	Delay or discontinue avelumab therapy Rule out sepsis Stress dose of IV steroids with mineralocorticoid activity IV fluids Consult endocrinologist If adrenal crisis ruled out, then treat as above for symptomatic endocrinopathy	

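### Section 6.9 leaves out the steroid exceptions that 5.2.3b and 5.2.4b-c allow at entry, so read literally an eligible patient on replacement or low-dose steroids should be taken off avelumab

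*Combined protocol and SAP*

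**What the plan says.** **Entry rules (section 5.2).** Criterion 5.2.3b accepts patients who need corticosteroid replacement if "steroids are administered only for the purpose of hormonal replacement and at doses" of no more than 10 mg prednisone equivalent per day. Criterion 5.2.4 excludes current immunosuppressive medication but lists exceptions. Item b is "Systemic corticosteroids at physiologic doses" (up to 10 mg/day prednisone or equivalent), and item c is "Steroids as premedication for hypersensitivity reactions (eg, CT scan premedication").

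**On-study rule (section 6.9, prohibited concomitant therapy).** The prohibited list covers the screening and treatment phase and includes "Systemic glucocorticoids for any purpose other than to modulate symptoms from an adverse event of suspected immunologic etiology". The section then sets the consequence for anyone needing a listed therapy, in these words: "in the assessment by the investigator, require the use of any of the aforementioned treatments for clinical management should be removed". What such patients leave is trial treatment. The closing sentence of 6.9 permits other medically necessary medications, which does not bring back anything on the list.

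**Related text.** Section 8.1 exempts from its Grade 2 discontinuation rule "hormone insufficiencies, that can be managed by replacement therapy". In Table 2, under symptomatic endocrinopathy, avelumab may resume after improvement, and "Subjects with adrenal insufficiency may need to continue steroids with mineralocorticoid component". Section 6.2 states that "a CT Chest with contrast or MRI will be performed on Cycle 4 (+/- 4 days) of Avelumab treatment". Section 15.4 defines the Phase II analysis population as registered subjects who received SBRT and at least 2 cycles of avelumab.

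**The concern.** Entry criteria and concomitant-medication rules should agree on which background drugs a trial patient may take. Here one section makes the patient eligible and another prohibits the same drug at the same time. A patient on physiologic replacement cannot comply with 6.9 by stopping a drug that is needed.

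Two things are at stake. The first is exposure: avelumab could be withheld or stopped for a reason that has nothing to do with tolerability or disease course. The second is consistency. Removal depends on the investigator's assessment, and section 16.4 provides for sites other than UCSD. One investigator may follow 5.2 and treat; another may follow 6.9 and not start, or stop. A patient stopped before the second cycle also drops out of the Phase II efficacy population.

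**Working it through.** The plan gives no figure to reproduce on this point. The check compares the texts and then works out what removal would cost per patient.

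**1. The rules side by side**

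| Steroid use | Section 5.2 | Section 6.9 |
|---|---|---|
| Hormone replacement, ≤10 mg/day prednisone equivalent | Allowed (5.2.3b) | Prohibited |
| Physiologic-dose systemic steroid, ≤10 mg/day | Allowed (5.2.4b) | Prohibited |
| Premedication for hypersensitivity, such as before CT | Allowed (5.2.4c) | Prohibited |
| Treatment of a suspected immune-related adverse event | Not addressed as such | Allowed |

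Topical, inhaled and intranasal steroids (5.2.3c, 5.2.4a) are not systemic and do not conflict with 6.9.

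**2. Do the two rules apply at the same time?** Yes. Criterion 5.2.4 concerns current use, and the 6.9 list covers screening as well as treatment. A deliberate tightening after enrolment would not need to reach back into screening.

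**3. Does any other section reconcile them?** No.
- The premedication text in section 7.1 concerns avelumab infusions and itself bars systemic corticosteroids.
- Steroid treatment of adverse events in section 8 fits the one exception in 6.9. It does not cover replacement that predates enrolment, low-dose maintenance or contrast premedication.

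**4. Cost per affected patient, assuming no dose delays**

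Inputs: 14-day cycles dosed on day 1, six cycles (6.3.1); first SBRT fraction 3 to 10 days after cycle 1 starts (6.3.2); 4 to 5 fractions every other day (6.5); follow-up counted from SBRT completion, with ±4 days at 6 weeks (section 10); chest imaging at cycle 4 ±4 days (6.2).

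- Dose days: 1 + 14 × (k − 1) for k = 1 to 6, giving 1, 15, 29, 43, 57, 71.
- SBRT start: 1 + 3 = day 4 to 1 + 10 = day 11.
- SBRT duration: 2 × (4 − 1) = 6 days or 2 × (5 − 1) = 8 days.
- SBRT completion: 4 + 6 = day 10 to 11 + 8 = day 19.
- 6-week CT: 10 + 42 = day 52 to 19 + 42 = day 61; with ±4 days, day 48 to 65.
- Cycle 4 scan: 43 ± 4 = day 39 to 47.

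| Point of removal | Doses given | Doses lost of 6 | In Phase II set (≥2 cycles and SBRT)? |
|---|---|---|---|
| Never started, or before cycle 2 (day 15) | 0–1 | 5–6 | No |
| Premedication at cycle 4 scan (day 39–47) | 3–4 | 2–3 | Yes |
| Premedication at 6-week CT (day 48–65) | 4–5 | 1–2 | Yes |

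Both scans fall after cycle 2, so premedication can shorten exposure but cannot change the analysis set. The analysis-set consequence arises only for replacement or low-dose use.

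**The case against.** The mismatch between 5.2 and 6.9 is hard to dispute; the arguments on the other side concern its weight.

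- **The supporting text is weak.** Section 8.1 speaks of hormone insufficiencies in general, and Table 2 deals with immune-related events whose steroid treatment already fits the 6.9 exception. This stands in part. These passages do not themselves conflict with 6.9; they show only that replacement was regarded as compatible with avelumab. The contradiction rests on 5.2 against 6.9.
- **A stricter rule on treatment than at entry can be deliberate.** The infusion premedication text shows an intent to limit steroids. That could explain a tighter rule for low-dose maintenance. It does not explain a ban that also covers screening, and it cannot work for replacement, which a patient cannot simply stop.
- **CT premedication is the weakest case.** A single dose before a scheduled scan may not count as a need for clinical management. MRI is an alternative at cycle 4, and the calendar row for 6 weeks reads CT or MRI, although 6.4 names only contrast CT. This stands, and premedication is the lesser part of the point.
- **Baseline steroid use is known at screening.** The realistic outcomes are treatment under 5.2 or not starting, rather than starting and then stopping before cycle 2. This is fair. Not starting still means no avelumab and no place in the analysis set.
- **No endpoint is shown to move.** The Phase I tolerability rule counts only discontinuations for treatment-related adverse events, and section 15.2 allows for 10% dropout. This also stands: the point demonstrates no bias in RFS and no change in error rates.

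**Conclusion.** The concern holds. Section 6.9 omits all three systemic-steroid allowances made at entry, no other section restores them, and the two rules apply to the same patient at the same time. The likeliest explanation is an exception left out of 6.9.

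The number of patients affected cannot be derived from the documents. Per patient, the cost ranges from 1 to 2 doses (removal at the 6-week CT) to 5 to 6 doses with exclusion from the Phase II set (not starting, or stopping before cycle 2). These figures assume a literal reading of 6.9, an investigator who judges the steroid to be required, and no dose delays. Sample size, power, significance level and the Phase I tolerability rule are unaffected. This should be corrected because the rule is wrong as written and costs little to repair, not because it threatens the primary result.

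**What to change.** Add to the glucocorticoid item in 6.9 the exceptions already in 5.2.3b and 5.2.4b-c:

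- hormone replacement or physiologic dosing up to 10 mg/day prednisone equivalent;
- premedication for hypersensitivity, for example before contrast CT.

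Then state that steroid use allowed at entry does not trigger removal from the treatment portion of the study.

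The cost is one wording amendment to 6.9. Sample size, visit schedule and data collection do not change.
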